4.3.1.3 Sensitivity analysis

4.3.1.4 No sensitivity analysis will be performed due to the discontinuation of the study after the futility analysis Supplementary analyses

While on-treatment estimand

A supplementary analysis will estimate the difference in mean slope of log10-transformed TKV during the on-treatment period. In this secondary analysis, TKV assessed more than 30 days after the last IMP administration will be excluded from the analysis. TKV assessed in randomized but not treated participants will also be excluded from the analysis.

Other analysis

Another analysis will explore a potential acute hemodynamic effect. In this supplementary analysis only TKV assessed at least 30 days after the first IMP will be included in the linear mixed effect model. TKV at baseline will be excluded from this analysis.

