### 9.4.1 Magnetic resonance imaging

- Magnetic resonance imaging will be performed at certified facilities and liver and kidney volumes calculated according to a separate protocol. Images will be reviewed/assessed by a central reader.

Magnetic resonance imaging will be performed at the following time points:

- Stage 1: During the screening period (at Visit 1 or Visit 2) and at Months 1, 9, and 18.
- Stage 2: During the screening period (at Visit 1 or Visit 2) and at Month 18.

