### 10.1 VISIT SCHEDULE

This is an outpatient study consisting of on-site visits. Additional, optional phone-call visits to monitor safety should be scheduled as often as deemed necessary by the Investigator. If a patient does not attend a scheduled visit, the study site personnel should contact the patient by telephone as soon as possible for rescheduling.

Scales and questionnaires should be completed before dosing and before clinical assessments by the Study Investigator or other healthcare provider(s).

Before any screening assessment is performed, information regarding the aims and methods of the study, its constraints and risks will be explained to the patient and a written summary in the form of an informed consent will be provided. The patient must sign and date the informed consent before screening and before patient demography is recorded.

Although the screening assessments for this study are grouped under the heading of a single visit in this protocol, it is possible for these to be performed over more than one site visit if necessary, as long as the screening visit window prior to Day -15 (run-in/Visit 2) is respected. Rescreening is possible in this study.

The study visits occur on the planned dates (relative to the first administration of IMP), as scheduled. The visit schedule should be adhered to within  $\pm 3$  days for the run-in period,  $\pm 7$  days for the double-blind core treatment period, and -7 to +21 days for the follow-up (off-treatment) period. If one visit date is skipped/missed/changed, the next visit should take place according to the original schedule.

Further details of procedures/assessments listed in the following sections are captured in the study flow charts ([Section 1.3](#) and [Section 1.4](#)).

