### **10.1.2 Treatment period - Month 0 to Month 24**

**Visit window:** The randomization visit (Day 1) should be performed 15 days after Visit 2 with the acceptable window of  $\pm 3$  days. Using Day 1 as reference, a time frame of  $\pm 7$  days is acceptable for Visits 4 to 12. (If one visit date is skipped/missed/changed, the next visit should take place according to the original schedule.)

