#### **10.1.2.1 Visit 3: randomization at Month 0/Day 1**

Screening assessments will be completed within the 30-day screening period. Eligibility will be reconfirmed prior to randomization/first dose IMP administration on Day 1 (based on results of assessments performed during the screening period, including evaluation of liver enzymes at the run-in visit and blood pressure at the baseline visit).

Patients will receive either placebo or venglustat, orally, at the clinic.

Patients will be instructed to record any missing doses of IMP and pain medication used in their patient diary. The patient should bring their diary and any remaining capsules to each clinic visit. The site staff will review the patient diary during each clinic visit and record excursions from treatment into the eCRF. The patient diary will be retrieved when the patient finishes their participation in the study.

The Randomization visit (Day 1) will include assessments and activities as listed in the study flow chart, [Section 1.3](#) and [Section 1.4](#), which should be done in the following order:

- Whenever possible, the following scales and questionnaires should be done prior to clinical interaction with the Investigator:
  - BPI ([Appendix E](#)),
  - BFI ([Appendix F](#)),
  - PGIS ([Appendix G](#)),
  - EQ-5D-5L ([Appendix H](#)).
- Review of concomitant medications.
- Review of current medical conditions, with AE/SAE reporting (if any).
- Collection of spot urine sample.
- Collection of home urine based on 24-hour collection.
- Reconfirmation of eligibility by the Investigator.
- Review daily symptom diary for completeness.
- Review of missed dose log for eligibility compliance.

- Abbreviated physical examination (focus on cardiac and respiratory systems, as well as any areas important for assessment of AEs if necessary).
- Vital signs.
- Laboratory assessments.
  - Chemistry and hematology.
- Biobanking blood sample (optional) collected prior to the start of IMP.
- Pharmacogenetic sample (optional).
- Urine pregnancy test (for WOCBP).
- Randomization via IRT.
- Dispense study medication.
- Blood sampling for PK analysis 3 hours post dose (Stage 1 only).
- If the patient is participating in the mGFR substudy, perform iohexol infusion and collect blood samples according to [Appendix L](#).
- Issue daily symptom diary and remind the patient that this should be completed daily until Visit 5.

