## **Secondary analysis**

A secondary analysis will estimate the difference in mean slope of  $\log_{10}$ -transformed TKV during the on-treatment period (while on treatment strategy). In this secondary analysis, TKV assessed more than 30 days after the last IMP administration will be excluded from the analysis. TKV assessed in randomized but not treated patients will also be excluded from the analysis. Any missing data during the on-treatment period will be considered “at random” in this secondary analysis, therefore no imputation will be required since the linear mixed effect model provides valid inference under missing at random assumption.

Another secondary analysis will explore a potential acute hemodynamic effect. In this secondary analysis, only TKV assessed from 1 month to 18 months will be included in the linear mixed effect model. TKV at baseline will be excluded from this secondary analysis.

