## **Appendix G Patient global impression of severity (PGIS)**

## Appendix H Patient global impression of change (PGIC)

## Appendix I EuroQol (EQ-5D-5L)

## Appendix J Statistical technical details

### Operating characteristics of the study design

Operating characteristics were assessed through extensive simulations. All simulations used the following assumptions on design and parameters:

- Sample size of 80 patients per arm in Stage 1 (randomized 1:1:1 to placebo, venglustat 8 mg or venglustat 15 mg) and of 160 patients per arm in Stage 2 (randomized 1:1 to placebo or venglustat).
- TKV assessed at screening, 1 month, 9 months, and 18 months in Stage 1; at screening and 24 months in Stage 2.
- eGFR assessed at baseline, 1 month, 3 months, and then every 3 months, both in Stage 1 and Stage 2.
- Mean slope of  $\log_{10}(\text{TKV})$  of 0.02764 (6.6%/year) in the placebo arm.
- Standard deviation for the residual error of TKV (on the  $\log_{10}$  scale) of 0.02566 and standard deviation for the random effect of slope of 0.01477.
- Mean slope of eGFR of -3.66 mL/min/1.73 m^2 per year in the placebo arm.
- Standard deviation for the residual error of eGFR of 6.34 and standard deviation for the random effect of slope of 1.98.
- Correlation between  $\log_{10}(\text{TKV})$  slope and eGFR slope of -0.35.
- Dropout rate of 10% at 2 years, assuming an exponential distribution for time to dropout.

Simulations were based on different scenarios regarding the true effect of venglustat on TKV and eGFR. Most scenarios assumed a 50% relative reduction in TKV growth rate and a 30% relative reduction in eGFR rate of decline for the venglustat 15 mg, and varying effect of venglustat 8 mg. They also assumed that the 15 mg dose was selected in Stage 2. These scenarios are presented in [Table 7](#). Additional scenarios assuming that the 8 mg dose was selected in Stage 2 were considered and are presented in [Table 8](#).

For each scenario, 10 000 trials were simulated. Each simulated trial was analyzed according to the procedure described in [Section 11.4.2](#).

- An interim analysis was performed when all patients from Stage 1 had TKV at baseline, 1 month and 9 months and 30% of patients also had TKV at 18 months (or had discontinued). Futility was declared at the interim analysis if the one-sided p-value from Multiple Comparison Procedure was  $>0.30$ .

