4.9.2 Interim futility analysis

An interim analysis for futility was performed when all participants from Stage 1 have completed the first 9 months of treatment and approximately 30% have completed 18 months of treatment with TKV available (or have prematurely discontinued).

The interim analysis was performed by the external independent statistician and was reviewed under the supervision of the DMC. The interim analysis primarily focused on the primary endpoint in Stage 1 (annualized rate of change in TKV) and stopping rules were based on this primary endpoint. Data monitoring committee also reviewed secondary efficacy endpoint (annualized rate of change in eGFR) and safety data (AEs, laboratory data, vital signs) available at the time of the interim analysis.

As per protocol, futility may be declared if the one-sided p-value of the primary endpoint at the interim analysis is >0.30. The one-sided p-value is determined from the Multiple Comparison Procedure described in Section 4.3.1.2. Based on simulations, it is expected that futility may be declared if the relative reduction versus placebo in TKV growth rate estimated at the interim analysis is approximately less than 15%. Probability to declare futility under different scenarios is presented in Section 5.6.1.

Of note, the futility rule is non-binding and provided as a guideline for the DMC but should not be considered as a strict stopping rule. In case the one-sided p-value observed at the interim analysis

is close to the pre-specified threshold, the DMC reviews the totality of data available at the time of interim analysis, including safety data (AEs, laboratory data, vital signs), and based on these data, may decide to overrule the futility rule.

If the DMC recommends continuing the study, then the Sponsor is informed of the recommendation and have no access to any unblinded results.

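### The acute-effect TKV analysis keeps only scans at least 30 days after first dose, which excludes 7 or 8 of the 15 days on which the Month 1 MRI is allowed

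*SAP*

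**What the plan says.** SAP 4.3.1.4 (Supplementary analyses, Other analysis) describes a linear mixed model meant to explore an acute hemodynamic effect. Its selection rule is: "In this supplementary analysis only TKV assessed at least 30 days after the first IMP will be included in the linear mixed effect model". The baseline scan is also left out.

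Protocol 11.4.2.1.1 (Secondary analysis) describes the same analysis, again without baseline, but selects by month: "only TKV assessed from 1 month to 18 months will be included in the linear mixed effect model".

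The timing of the Month 1 scan is fixed by these places in the protocol:

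- Section 9.4.1 gives the MRI schedule: "Stage 1: During the screening period (at Visit 1 or Visit 2) and at Months 1, 9, and 18".
- The Stage 1 flow chart (1.3) puts Visit 4, Month 1, on Day 30 with a window of ±7 days.
- Section 10.1 times visits from first dose: "The study visits occur on the planned dates (relative to the first administration of IMP), as scheduled". Section 10.1.2 sets the ±7 days for Visits 4 to 12: "Using Day 1 as reference, a time frame of" ±7 days.
- Section 10.1.2.1 puts first dose on Day 1: "Eligibility will be reconfirmed prior to randomization/first dose IMP administration on Day 1".

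**The concern.** The cut-off sits almost at the centre of the visit window, so a scan done on time can pass or fail according to a few days of scheduling. Month 1 is the only scheduled scan between baseline and Month 9. With baseline already removed, a patient who loses Month 1 keeps at most Months 9 and 18. A patient with no Month 18 scan either is left with Month 9 alone and adds almost nothing to the slope.

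The stake is avoidable loss of precision in the one slope model meant to set aside an acute volume change. There is also an unresolved difference between the SAP and the protocol over which scans belong in it. No bias is claimed.

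**Working it through.** **Step 1. Count the permitted days.** Day 30 ±7 gives Days 23 to 37, which is 15 days. With first dose on Day 1, a scan on Day d is d − 1 days after first dose, so compliant scans lie 22 to 36 days after it.

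- Elapsed-day reading (d − 1 ≥ 30): Days 23 to 30 fail, 8 of 15 (53%). The on-target Day 30 scan fails because it is 29 days after dosing.
- Study-day reading (d ≥ 30): Days 23 to 29 fail, 7 of 15 (47%).

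The SAP does not say which reading applies.

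**Step 2. Look for text that would save the scan.** SAP 5.4 has a wide Month 1 analysis window (Table 12, D2 to D60) and a planned-visit rule for TKV, but both govern by-visit summaries, not slope models. For slope analyses, the same section says assessments at planned and unscheduled visits are all used. Nothing exempts the nominal Month 1 scan from the 30-day rule. The protocol's own list of TKV times in Appendix J uses 1 month as a label for the scheduled scan: "TKV assessed at screening, 1 month, 9 months, and 18 months in Stage 1".

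**Step 3. Size the loss.** The plan states no figure for this, so there is none to reproduce. Inputs:

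- residual SD 0.02566 and slope SD 0.01477 on the log10 scale (SAP section 2);
- intercept SD 0.13284 (simulation code, SAP 5.5), with intercept-slope covariance set to zero;
- 80 patients per arm;
- scans at 0.083, 0.75 and 1.5 years, no baseline.

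Two quantities are assumed and varied: L, the fraction of patients whose Month 1 scan is excluded, and the share of patients with a Month 18 scan (100%, 60% or 30%). The 30% is a floor. It was the futility trigger, "approximately 30% have completed 18 months of treatment with TKV available", whereas SAP 4.1 uses everything available at database lock.

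For a patient with scan times t, let X have rows (1, t) and V = X D Xᵀ + 0.02566² I, where D = diag(0.13284², 0.01477²). Summing Xᵀ V⁻¹ X over an arm gives the information matrix J. The SE of the slope difference between two arms is √(2 × [J⁻¹]₂₂).

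| Month 1 scans lost | SE, 100% with Month 18 | SE, 60% | SE, 30% | Rise in SE |
|---|---|---|---|---|
| none | 0.00467 | 0.00554 | 0.00666 | – |
| 10% | 0.00483 | 0.00575 | 0.00693 | 3.4 / 3.7 / 4.1% |
| 25% | 0.00511 | 0.00611 | 0.00742 | 9.3 / 10.1 / 11.4% |
| 7/15 | 0.00561 | 0.00677 | 0.00836 | 20.0 / 22.0 / 25.5% |
| 8/15 | 0.00579 | 0.00702 | 0.00873 | 23.9 / 26.6 / 31.1% |
| all (bound) | 0.00800 | 0.01030 | 0.01455 | 1.71 / 1.86 / 2.18-fold |

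The 7/15 and 8/15 rows are what would be lost if scans were spread evenly over the window.

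**Step 4. Put it in patients and in percentage points.** Equivalent patients per arm = 80 × (SE with none lost / SE with L lost)², from unrounded SEs. This gives 55.6 / 53.7 / 50.8 at 7/15 and 52.1 / 49.9 / 46.6 at 8/15.

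The approximate 95% CI half-width, in points per year, is 1.96 × SE × ln(10) × 100:

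| Share with Month 18 | None lost | 7/15 lost | 8/15 lost |
|---|---|---|---|
| 100% | 2.11 | 2.53 | 2.61 |
| 60% | 2.50 | 3.05 | 3.17 |
| 30% | 3.00 | 3.77 | 3.94 |

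For scale, planned placebo growth is 10^0.02764 − 1 = 6.57% per year, so the design's 50% reduction is 3.29 points. With about half the scans lost, the half-width exceeds that only at the 30% floor.

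**Step 5. Check what the full window would cost.** Keeping every Month 1 scan, with all patients at Month 18, the SE is 0.00462, 0.00466 or 0.00471 if those scans are all done 22, 29 or 36 days after first dose. Using the intercept-slope covariance of 0.000105 from protocol Appendix J changes the SE ratios by less than 0.002.

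**The case against.** The best counter-argument is about importance. This is one exploratory analysis with descriptive p-values (SAP 4.6), in an SAP version written after the study was stopped for futility, and no decision rests on it. That is correct and limits the weight of the point. It does not make the rule right.

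It can also be said that 30 days is a fair rendering of 1 month, since the flow chart equates Month 1 with Day 30, and that the 8-day count depends on an elapsed-day reading. The SAP counts exposure inclusively (4.7.1), which favours study days. That reading is plausible, but it still rejects 7 of the 15 compliant days. Appendix J lists simulation assumptions and does not define this analysis, so it supports the scheduled-scan meaning of 1 month without settling it.

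A count of days is not a count of scans. This stands: the larger losses need an even spread of dates, which the documents neither support nor exclude. Patients with Months 9 and 18 still contribute, the primary model keeps all Month 1 scans, and by-visit summaries can still show Month 1 by arm.

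Finally, 30 days might have been chosen as a minimum exposure. The documents give no such reason, and the protocol starts the analysis at 1 month while its visit window allows Day 23.

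**Conclusion.** The concern holds. As written, the rule excludes Month 1 scans that comply with the protocol on 7 or 8 of 15 permitted days, depending on an unstated day count, and it is narrower than the protocol's 1-to-18-month analysis if 1 month there means the scheduled scan. The day counts are exact, given first dose on Day 1.

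The loss of precision is conditional on scan dates that the documents do not give: an SE 3-4% larger if 10% of Month 1 scans are lost, 9-11% at 25%, and 20-31% at about half, which is like having 56 to 47 patients per arm instead of 80. The 1.7 to 2.2-fold figure is a bound, not an expectation. These figures rest on the design's variance components and on 30% to 100% of patients having Month 18.

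The effect is confined to a supplementary estimate. The primary TKV test, its power and its type I error are untouched. The rule should be corrected because it gives up precision for no stated reason.

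**What to change.** Replace the 30-day rule in SAP 4.3.1.4 with one tied to the visit window: include all TKV assessments, scheduled or unscheduled, on or after study Day 23, where Day 1 is the day of first IMP, and exclude baseline. State the Day 1 convention in that sentence, because SAP 5.4 sets D1 for efficacy windows at randomization. This keeps all 15 permitted days, treats scheduled and unscheduled scans alike as SAP 5.4 asks for slope analyses, and removes the day-count ambiguity.

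Reconcile the wording with protocol 11.4.2.1.1, and report by arm how many Month 1 scans enter the model. The cost is one sentence in the SAP and one count in the output. No new data are needed.

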4.3.1.5 Subgroup analyses

To assess the homogeneity of the treatment effect across various subgroups, analyses will be performed on the primary endpoint across the following subgroups (categories with fewer than 5 participants may be combined with other categories):

- Age group (<40, and ≥40 years)
- Gender (Male, Female)
- Actual ADPKD progression rate (1C versus 1D versus 1E) at baseline
- Region (North America, Europe, China, Japan, Republic of Korea, Rest of the World)
- eGFR (CKD-EPI equation) at screening (45 to <60, 60 to <75, 75 to <90)
- Prespecified medical history of Hypertension (Yes/No)

The linear mixed effect model described as primary analysis will be repeated for each of the subgroups as appropriate. Subgroup factor-by-time interaction, treatment-by-subgroup factor interaction and treatment-by-subgroup-by-time interaction will be added in the primary model. For subgroup analyses by Mayo Imaging Classification, the linear mixed effect model will not include the fix effects of Mayo Imaging Classification nor Mayo Imaging Classification * time interactions. Forest plots of venglustat 8 mg and venglustat 15 mg relative reduction versus placebo and 95% CI will be presented.

4.3.1.6 Description of missing data

In order to explore missing data patterns for TKV in the primary efficacy analysis, number and percentage of participants in each of the following categories will be presented by study intervention group and displayed separately for participants on treatment at the time of Month 18 visit versus participants with permanent intervention discontinuation prior to Month 18:

- Pattern 1: Participants without post-baseline TKV assessment.
- Pattern 2: Participants with at least one post-baseline TKV assessment but not at Month 18.
- Pattern 3: Participants with TKV assessment at Month 18.

4.3.2 Combined Stage 1 and Stage 2

4.3.2.1 Definition of endpoint(s)

In combined Stage 1 and Stage 2, the primary efficacy endpoint is the annualized rate of change in eGFR (CKD-EPI equation).

The primary estimand will be the difference in mean slope of eGFR estimated from baseline to 24 months in all randomized population, regardless of whether or not participants completed the treatment period. This estimand corresponds to a "treatment policy strategy".

4.3.2.2 Main analytical approach

The analysis of eGFR will be similar to those of TKV, with the exception that no log transformation will be used for eGFR (see Section 4.3.1.2).

Primary analysis in Stage 2 will combine all data from Stage 1 and Stage 2 available from baseline to the end of the 24-month double-blind core treatment period. Primary analysis will include all observed eGFR data in randomized participants, regardless of whether or not participants completed the treatment period (treatment policy strategy). Participants who prematurely and permanently discontinue study medication will be requested to obtain eGFR at 24 months.

No imputation of missing data will be performed.

4.3.2.3 Sensitivity analysis

No sensitivity analysis will be performed due to the discontinuation of the study after the futility analysis.

4.3.2.4 Supplementary analyses

While on-treatment estimand

A supplementary analysis will estimate the effect of venglustat while participants are still on treatment. eGFR assessed more than 30 days after the last IMP administration will be excluded from the analysis. eGFR assessed in randomized but not treated participants will also be excluded from the analysis.

Secondary analysis of eGFR

Descriptive summary of eGFR by analysis visit will be provided on the secondary Stage 2 ITT population (ie, all participants from Stage 2 with eGFR between 30 and 44.9 mL/min/1.73 m² at screening) (see Section 3).

Time to Event analysis

Time to confirmed reduction in eGFR (local or central assessment using CKD-EPI formula) will be summarized in terms of cumulative incidence probabilities of occurrence with 95% CI as well as the number of participants at risk, number of participants censored and number of events at key time points (Month 1, Month 3, Month 6, Month 9, Month 12, Month 18, Month 21, Month 24) using the Kaplan-Meier estimates. In addition, Kaplan-Meier curves will be provided for each treatment arm.

- Time to confirmed 30% (resp. 40%) reduction in eGFR is defined as: the time from the date of randomization to the date of first eGFR assessment in case of 2 consecutive eGFR assessment with an observed reduction in eGFR from baseline of at least 30%.
 - If reduction in eGFR from baseline is less than 30% (resp. 40%) or if reduction is not observed at 2 consecutive visits before end of study, the participant will be censored at the date of the last participant's eGFR assessment for the combined Stage 1 and Stage 2 analysis.

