--	--

ASSESSMENT SCHEDULE	
Stage 1
 
Efficacy assessments: MRI during screening period (at Visit 1 or Visit 2), Months 1, 9, and 18. eGFR (CKD-EPI) at screening, run-in, baseline, Month 1, Month 3, and then every 3 months.
 
Safety/tolerability assessments: Vital signs, physical examination, clinical laboratory evaluation will be performed at all visits. Ophthalmological assessments will be performed at Months -0.5, 6, 12, 18, and 24. Beck Depression Inventory-II will be assessed at Months -0.5, 3, and then every 3 months.
 
Biomarker assessments: Screening, Months 1, 6, 12, 18, 24, and at 30 days follow-up (Month 25).
 
PK assessments: Blood samples for plasma venglustat concentrations assessment will be collected in all patients at following visits:
 

• Day 1: 3 (±1) hour post dose.

• Month 1: pre-dose and 3 (±1) hours post dose.

• 6 months and 18 months: pre-dose sample.

 
Patient Reported Outcome (PRO) Assessments:
 
Pain (BPI) and fatigue (BFI) data will be collected at the baseline visit and at each study visit prior to administration of procedures and the disease and treatment discussion with the patients. Patient global impression of severity will be collected at run-in, baseline and Months 3, 12, 18, and 24. Patient global impression of change will be collected at Months 3, 12, 18, and 24. Health status (EQ-5D-5L) will be collected at baseline and Months 3, 6, 12, 18, and 24.
 
Daily diary data on symptoms of ADPKD (pain: BPI Item 3, fatigue: BFI Item 3, and nocturia) will be entered by the patients for specified consecutive days during the administration period prior to Baseline visit, from Baseline visit to Month 3, and prior to the site visit at Months 12, 18, and 24.
 
Patients who prematurely and permanently discontinue study medication should complete rapidly (within 7 days) an end of treatment assessment visit. End-of-treatment visit should include all procedures of Visit 12 and additionally a PK sample should be collected. In 30 days, a Follow-up visit should be performed. Investigator should ask patient to continue study visits for safety and efficacy assessments up to and including the last scheduled visit, if possible. If the patient refuses to attend all scheduled visits and to continue answering all PRO questionnaires, Investigator should ask the patient to continue answering questions of "Daily symptoms of ADPKD" diary, and also return to the site at Month 18 to have at least MRI performed, and at Month 24 to have at least blood sample (for eGFR) collected. Other assessments planned at Month 18 and/or Month 24 should also be done if possible.
 
Stage 2
 
Efficacy assessments: MRI during screening period (at Visit 1 or Visit 2) and Month 18. eGFR (CKD-EPI) at screening, run-in, baseline, Month 1, Month 3, and then every 3 months.
 
Iohexol will be administered in a substudy in approximately 15% of patients at the baseline visit, Months 12 and 24 to evaluate mGFR.
 
Safety/tolerability assessments: Vital signs, physical examination, clinical laboratory evaluation will be performed at all visits. Ophthalmological assessments will be performed at Months -0.5, 6, 12, 18, and 24. BDI-II will be assessed at Months -0.5, 3, and then every 3 months.
 
Biomarkers: Screening, Months 6, 12, 18, 24, and at 30 days follow-up (Month 25).

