## **6.2 DURATION OF STUDY PARTICIPATION**

### **6.2.1 Duration of study participation for each patient**

The maximum study duration per patient will be approximately 26 months.

This will consist of a screening period of up to 30 +3 days (initial screening period of up to 15 +3 days and single-blind placebo run-in period of 15 ±3 days), followed by a blinded study core treatment period of 24 months and a 30-day follow-up visit (for patients not participating in the potential long-term extension study) after the final dose of investigational medicinal product (IMP).

Patients who completed 24 months of treatment in EFC15392 study may be given the option to enroll into an open-label long-term extension study LTS15823 (additional 24 months of treatment with 15 mg venglustat [ie, as specified in the EFC15392 protocol the dose selected for Stage 2 of EFC15392 study during unblinded review by the DMC of the aggregated safety data for 150 patients who have completed at least 1 month of treatment in EFC15392 study]).

The last study visit:

1. for patients who elect to enter the potential long-term extension study upon completion of 24 months of treatment in EFC15392 study will be Visit 12 (Month 24)
2. for patients who complete the treatment in EFC15392 study and elect not to enter this potential extension study will be Visit 13 (Month 25)
3. for patients who permanently discontinue medication and continue for all the remaining visits will be Visit 12 (Month 24) if they continue for all the remaining visits, or it will be their premature follow-up visit.

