### **10.1.3 Follow-up visit - Visit 13/Month 25 (Day 750)**

Not applicable for patients who may be eligible for a potential long-term extension study after completion of 24 months of treatment.

**Visit window:** The Follow-up Visit (Day 750) can be performed within a -7 to +21 days window.

The following activities will be performed:

- Review of current medical conditions, with AE/SAE reporting (if any).
- Review of current and prior medications.
- Collection of spot urine sample.

- Abbreviated physical examination (focus on areas important for assessment of AEs if necessary).
- Record of body weight measurement.
- Vital signs.
- Laboratory assessments (Chemistry only).
- Blood sampling for GSL markers.
- Blood sampling for biomarker analysis in Stage 1. In Stage 2, only if to be done following analysis of Stage 1 samples.

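### The Month 24 incidence of confirmed eGFR decline is understated, because extension entrants stay at risk up to a value that this study has no planned visit to confirm

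*SAP*

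**What the plan says.** SAP 4.3.2.4 (Time to Event analysis) counts an event "in case of 2 consecutive eGFR assessment with an observed reduction in eGFR from baseline of at least 30" percent (40 for the second endpoint) and dates it at the first of the two assessments, measured from randomization. If the threshold is not reached, or "if reduction is not observed at 2 consecutive visits before end of study", then "the participant will be censored at the date of the last participant's eGFR assessment". Local and central values both count. Kaplan-Meier estimates are requested at listed time points, ending with Months 18, 21 and 24.

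The protocol's assessment schedule gives "eGFR (CKD-EPI) at screening, run-in, baseline, Month 1, Month 3, and then every 3 months". Protocol 6.2.1 makes Visit 12 (Month 24) the last visit for completers who enter the extension, and Visit 13 (Month 25) the last visit for completers who do not. Visit 13 includes chemistry, and so a creatinine, but Section 10.1.3 says it is "Not applicable for patients who may be eligible for a potential long-term extension study after completion of 24 months of treatment". Footnote b of the flow charts waives it for patients who screen for the extension within 30 days after Month 24.

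The SAP has no rule for a low last value that was not repeated. It does not say whether a Visit 13 or LTS15823 value may confirm a Month 24 decline.

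**The concern.** With the event dated at the first of two low values, a participant can have an event at a given visit only if a later eGFR exists. The SAP's censoring rule ignores this. An extension entrant adds to the Month 24 denominator but cannot add to its numerator. Two completers with the same low Month 24 value can be treated differently: one becomes an event through Visit 13, and the other is censored because he or she rolled over.

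What is at stake is the final point of the curve. Time to confirmed 30% and 40% reduction are exploratory endpoints of the protocol, and the Month 24 figure is the one a reader is likely to cite. Its shortfall depends on extension enrolment, not on kidney function.

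**Working it through.** **Checking the model.** The documents give no expected incidence for this endpoint. The nearest stated figures on the same eGFR model are the Scenario 2 operating characteristics (SAP 5.6.1, Table 15). I recomputed them from the mixed-model slope variances with exponential dropout, the maximum of the three contrasts, futility at one-sided p > 0.30, and thresholds 0.04, 0.001, 0.049 and 0.01:

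| | Stated | Recomputed |
|---|---|---|
| TKV, end of Stage 1 | 89.0% | 88.9% |
| eGFR, end of Stage 1 | 5.1% | 4.8% |
| eGFR, overall | 87.0% | 86.9% |
| Futility | 3.1% | 3.0% |

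The eGFR model is therefore understood as the sponsor used it.

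**Formula.** Let F21 and F24 be the true cumulative incidences at Months 21 and 24, and q the share of completers who roll over, independently of eGFR. On nominal visit times the Month 24 risk set is unchanged, but only a fraction (1 - q) of Month 24 events can be confirmed. Hence

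F24 under the SAP rule = F21 + (1 - q)(F24 - F21), and relative shortfall = q(F24 - F21)/F24.

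**Inputs.** From SAP 5.6.1: placebo slope -3.66 per year, slope SD 1.98, residual SD 6.34, dropout 10% at 2 years. From Protocol Appendix J: intercept variance 106.81, intercept-slope covariance 5.36. From SAP 4.1 and the visit schedule: baseline is the mean of three pre-treatment values. Assumed, because the documents do not give them: mean baseline eGFR of 60, 68 or 75, and roll-over of 20% to 100%.

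**Simulated incidence (%) of the 30% decline, nominal visits** (300,000 draws per setting; relative shortfall in brackets):

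| Mean baseline | F21 | F24, all confirmable | SAP rule, q = 20% | 50% | 80% | 100% |
|---|---|---|---|---|---|---|
| 60 | 3.98 | 5.74 | 5.41 (5.8%) | 4.86 (15.4%) | 4.33 (24.6%) | 3.98 (30.7%) |
| 68 | 2.15 | 3.30 | 3.08 (6.7%) | 2.75 (16.9%) | 2.39 (27.8%) | 2.15 (35.0%) |
| 75 | 1.15 | 1.86 | 1.72 (7.8%) | 1.52 (18.4%) | 1.29 (30.5%) | 1.15 (38.0%) |

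The formula agrees. For baseline 68 and q = 0.8: 0.8 × (3.30 - 2.15)/3.30 = 27.9%, against 27.8% simulated. At 100% roll-over the Month 24 estimate is simply the Month 21 estimate. For the 40% decline the shortfall is 8-50% relative over the same range of q, but at most 0.4 percentage points.

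**Actual dates.** The SAP uses assessment dates, and visits have a ±7-day window. Entrants then leave the risk set during that window, which offsets part of the loss unless all roll over: about 9-13%, 20-28% and 30-41% at 50%, 80% and 100%.

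**Does Visit 13 count?** The Month 24 window in SAP 5.4, Table 12 runs from D676 to D765 and so contains Day 750, the Visit 13 target. If that window were applied to this endpoint, Visit 13 would not be a separate visit and the 100% column would apply to all completers. The SAP does not say.

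**Testing the repairs.** On nominal visits, counting each participant as at risk only to the last visit followed by a further eGFR gives, at 50% and 80% roll-over, 5.80% and 5.78% (true 5.74%), 3.38% and 3.38% (true 3.30%), and 1.90% and 1.87% (true 1.86%). On actual dates with ±7-day visits, n = 240 and 80% roll-over, censoring at the penultimate date gives about 8.1% by the end of the Month 24 window, against a true 3.6% and 2.8% under the SAP rule. It also distorts Month 21 (3.4% against 2.4%).

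**The case against.** The strongest reply is that little rests on this. The endpoint is exploratory, the SAP analysis is supplementary and Kaplan-Meier only, and it lies outside the multiplicity procedure. The trial was also stopped. First randomization was 11 February 2019 and the DMC reviewed futility on 14 May 2021, 27 months later, so only participants randomized in about the first 27 - 24 = 3 months could have had Month 24 by then. Stage 2 had no post-baseline MRI, which was planned at Month 18. Any extension entrants are thus early Stage 1 completers. All of this stands. By the formula, a small Month 24 risk set does not change the proportional shortfall, but it makes sampling error large beside it.

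Three stronger readings are tempting, and the documents do not support them.

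- **That extension entrants can never have a confirmed decline.** A decline first seen by Month 21 is confirmed at the next planned visit, including Month 24. Local values count, and a participant screened for the extension between Visits 12 and 13 has a later last visit, so a few Month 24 declines may also be confirmed.
- **That the stop causes a similar loss at Months 12 and 18.** Protocol 10.3.4 gives patients who stop treatment an end-of-treatment visit within 7 days with all Visit 12 procedures, then a 30-day follow-up with all Visit 13 procedures. That pair of creatinines can confirm.
- **That the comparison of arms is biased.** It is biased only if roll-over or late decline differs by arm, and nothing in the documents shows that.

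**Conclusion.** The point holds in a narrow form. For participants who enter LTS15823, a decline first seen at Month 24 has no planned confirmation in this study, yet they are counted as at risk up to that value. The Month 24 incidence of the 30% decline is understated by about 15-18%, 25-31% and 31-38% (relative) at 50%, 80% and 100% roll-over, or 0.3 to 1.8 percentage points. These sizes rest on the sponsor's placebo eGFR parameters, an assumed mean baseline of 60 to 75, nominal visit times, roll-over unrelated to eGFR, and Visit 13 being allowed to confirm for the others. The direction does not depend on those values. Estimates up to Month 21 are unaffected by roll-over. This is a defect in one descriptive estimate. It does not touch the primary eGFR slope analysis.

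**What to change.** Simplest: in SAP 4.3.2.4, make Month 21 the last reported Kaplan-Meier time point and flag Month 24 as not fully confirmable.

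If Month 24 is to be kept, run the analysis on nominal visit times, state that Visit 13 is a visit in its own right and may confirm a Month 24 decline, and count each participant as at risk only up to the last visit that was followed by a further eGFR. If every completer rolls over, Month 24 cannot be estimated this way and the curve ends at Month 21.

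Two repairs should be avoided. Censoring at the penultimate actual date overshoots, as shown above. Using LTS15823 values only where the last value is low makes confirmation depend on the outcome. Under the at-risk rule just described, entrants with a low Month 24 value would become events while the others left the risk set. Those values would also be taken on open-label venglustat, including in former placebo patients.

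The cost is a sentence or two in the SAP and a small change to the derivation, with no new data. The price is the loss of the Month 24 estimate, or a smaller risk set and wider interval there.
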